Efficacy Analyses: Individual BOR, duration of response and PFS will be listed using RECIST v1.1 criteria in solid tumors and investigator assessed revised IWG criteria in lymphomas. BOR outcomes will be tabulated by tumor type and treatment arm. The ORR and PFS rate (eg, at 24 weeks) and the corresponding confidence interval will be provided by tumor type and treatment. The duration of response and PFS will be estimated by Kaplan-Meier methodology by tumor type, depending on data availability. PFS rates at 24 weeks will be similarly estimated, based on Kaplan-Meier methodology. Presentations of efficacy will include subjects in cohort expansion and subjects in dose escalation matching those in cohort expansion by tumor type and treatment. Individual changes in the tumor burden over time will be presented graphically within a tumor type. Landmark overall survival will also be assessed as part of exploratory efficacy analysis, by Kaplan-Meier plots and medians for each tumor type.

[REDACTED]

[REDACTED]

[REDACTED]

[REDACTED]

[REDACTED]

TABLE OF CONTENTS

TITLE PAGE	
DOCUMENT HISTORY	
SYNOPSIS	
TABLE OF CONTENTS	
[REDACTED]	
1.2 Research Hypothesis	34
1.3 Objectives(s)	34
1.3.1 Primary Objectives	34
1.3.2 Secondary Objectives	34
[REDACTED]	
1.4 Product Development Background	35
1.4.1 Pharmacology	35
1.4.2 Toxicity	35
1.4.3 Clinical Pharmacology and Safety	36
1.4.3.1 Pharmacokinetics of urelumab and nivolumab	38
1.4.4 Immunogenicity of Urelumab	39
1.5 Overall Risk/Benefit Assessment	39
2 ETHICAL CONSIDERATIONS	41
2.1 Good Clinical Practice	41
2.2 Institutional Review Board/Independent Ethics Committee	42
2.3 Informed Consent	42
3 INVESTIGATIONAL PLAN	43
3.1 Study Design and Duration	43
3.1.1 Screening Period	43
3.1.2 Treatment Period	43
3.1.3 Clinical/Safety Follow-up	44
3.1.4 Survival/Long-Term Follow-up	44
3.1.5 Dose Escalation	45
3.1.6 Cohort Expansion	48
3.1.6.1 Stage 1 Cohort Expansion	49
3.1.6.2 Stage 2 Cohort Expansion	50
3.2 Post Study Access to Therapy	50
3.3 Study Population	50
3.3.1 Inclusion Criteria	50
3.3.2 Exclusion Criteria	58
3.3.3 Women of Childbearing Potential	61
[REDACTED]	

3.5 Discontinuation of Subjects from Treatment.....	63
3.5.1 Treatment Beyond Disease Progression	64
3.5.1.1 Discontinuation due to further progression	64
3.5.1.2 Assessment schedule for the subjects with post-progression treatment	65
3.6 Post Study Drug Follow-up	65
3.6.1 Withdrawal of Consent	65
3.6.2 Lost to Follow-Up	65

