3.3.1 Inclusion Criteria

1) Signed Written Informed Consent

- a) The subject must sign the informed consent form prior to the performance of any study-related procedures that are not considered part of standard of care.

2) Target Population

- a) Subjects must have histologic or cytologic confirmation of a malignancy that is advanced (metastatic and/or unresectable):
 - i) Dose Escalation:
 - (1).All solid tumor and B-cell NHL histologies will be permitted during dose escalation, except for subjects with primary CNS tumors, CNS lymphoma or with CNS metastases as the only site of active disease.

(2). Subjects must have received and then progressed, or been intolerant to, at least one standard treatment regimen in the advanced or metastatic setting, if such a therapy exists. Subjects who refuse or are ineligible for standard therapy will be allowed to enroll provided their refusal/ineligibility is documented in medical records.

ii) Cohort Expansion

(1). The following tumor types will be permitted during cohort expansion:

- a. Non Small Cell Lung Cancer (NSCLC). No prior anti-PD-1/anti-PD-L1 therapy
 - i. Must have recurrent or progressive disease during or after platinum doublet-based chemotherapy for advanced or metastatic disease OR must have recurrent or progressive disease within six months after completing platinum-based chemotherapy for local disease.
 - ii. Subjects with non-squamous histology must have known EGFR and ALK status.
 - iii. Subjects with an activating EGFR mutation must have received an EGFR tyrosine kinase inhibitor.
 - iv. Subjects with an ALK translocation must have received an ALK inhibitor.
- b. Melanoma(MEL)
 - i. Not applicable.
 - ii. Subjects must have known BRAF V600 mutation status or consent to BRAF V600 mutation testing per local institutional standards during the Screening Period.
 - iii. Histologically confirmed unresectable Stage 3 or Stage 4 melanoma as per American Joint Committee on Cancer (AJCC) staging system
 - iv. Treatment naive subjects (ie, no prior systemic anticancer therapy for unresectable or metastatic melanoma).
 1. Note: Prior adjuvant or neoadjuvant melanoma therapy is permitted if it was completed at least 4 weeks or 5 half-life times (whichever is shorter) prior to randomization and all related adverse events have either returned to baseline or stabilized.
- c. Head and Neck Squamous Cell Carcinoma (SCCHN)

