 - i. Histologically confirmed incurable locally advanced, recurrent or metastatic SCCHN (oral cavity, pharynx, larynx), stage III/IV and not amenable to local therapy with curative intent (surgery or radiation therapy with or without chemotherapy).
 - ii. Confirmation of tumor HPV status: Prior testing results are acceptable if known. If tumor HPV status is unknown, subjects must consent to allow their submitted archived tumor tissue sample in the form of block or unstained slides to be tested for confirmation of tumor HPV status.
 - iii. Tumor progression or recurrence within 6 months of last dose of platinum therapy in the adjuvant (ie, with radiation after surgery), primary (ie, with radiation), recurrent, or metastatic setting. Clinical progression after platinum therapy is an allowable event for entry and is defined as progression of a lesion at least 10 mm in size that is amenable to caliper

measurement (eg, superficial skin lesion as per RECIST 1.1) or a lesion that has been visualized and photographically recorded with measurements and shown to have progressed.

- iv. Prior curative radiation therapy must have been completed at least 4 weeks prior to study drug administration. Prior focal palliative radiotherapy must have been completed at least 2 weeks before study drug administration.
- d. Tumor Biopsy confirmation of relapsed or refractory DLBCL, or transformed lymphoma (TL), prior to the initiation of study drug.
 - i. TL is limited to DLBCL. Subjects with Grade 3b follicular lymphoma are excluded.
 - ii. DLBCL or TL should be pathologically confirmed by standard immunohistochemical or flow cytometric techniques.
 - iii. Documentation of the above should be present in the subject's medical record.
 - iv. Prior treatment as defined below;
 - 1. Subjects with relapsed DLBCL or TL after high-dose conditioning chemotherapy and ASCT, or
 - 2. Subjects with relapsed or refractory DLBCL or TL after at least 1 prior multi-agent chemotherapy regimen if ASCT ineligible. Ineligibility for ASCT will be determined using local institutional criteria.

Definition of Relapsed DLBCL

- the appearance of new lesions > 6 months after obtaining a CR
- an increase $\geq 50\%$ in the size of previously involved sites > 6 months after completing planned therapy

Definition of Refractory DLBCL

- $< 50\%$ decrease in lesion size after planned therapy,
- the appearance of new lesions during therapy or < 6 months after completion of planned therapy

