8.4.2 Efficacy Analyses

Individual best overall response (BOR), duration of response and PFS will be listed using RECIST v1.1 and IWG criteria, as appropriate. BOR outcomes will be tabulated by disease type and treatment (eg, with a column for each dose/regimen combination). The objective response rate (ORR) and PFS rate (eg, at 24 weeks) and corresponding confidence interval will be provided by tumor type and treatment. The duration of response and PFS will be estimated by Kaplan-Meier (K-M) methodology by disease type, depending on data availability. PFS rates at 24 weeks will be similarly estimated, based on K-M methodology. ORR, duration of response and PFS analyses will include subjects in the cohort expansion phase and subjects in dose escalation matching those in cohort expansion by disease type and treatment. Individual changes in the tumor burden over time may be presented graphically within a disease type. Landmark overall survival will be assessed as part of exploratory efficacy analysis, using Kaplan-Meier plots and the median (as measured using Kaplan-Meier Method) for each tumor type.

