## **6.2 Treatment Regimens**

Refer to [Table 2](#) and [Table 4](#) for treatment arms explored in this trial. Some of these arms might not have any subjects.

Certain analyses (eg, PFS and DOR) may include subjects in the dose escalation phase and subjects in the cohort expansion phase matched by disease type and regimen.

The treatment group “as assigned” will be retrieved from the IVRS system, if applicable. The treatment group “as treated” will be the drug combination that the subject actually received during the study, even if it is not the same as the arm that was assigned by IVRS. Unless otherwise specified, the safety analysis will be based on “as treated”.

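### Pooling dose-escalation subjects into the expansion efficacy analyses by disease type and study regimen only can mix pretreated subjects into the treatment-naive melanoma estimates

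*Protocol*

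**What the plan says.** **Pooling rule.** Protocol 8.4.2 says, of the analyses of ORR, PFS and duration of response, that they "will include subjects in the cohort expansion phase and subjects in dose escalation matching those in cohort expansion by disease type and treatment". The Synopsis (Efficacy Analyses) agrees: "Presentations of efficacy will include subjects in cohort expansion and subjects in dose escalation matching those in cohort expansion by tumor type and treatment". SAP 6.2 is softer. Certain analyses, with PFS and DOR as its examples, *may* include "subjects in the dose escalation phase and subjects in the cohort expansion phase matched by disease type and regimen"; ORR is not named there.

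**What treatment means.** Protocol 8.4.2 uses the word for the study regimen: "BOR outcomes will be tabulated by disease type and treatment (eg, with a column for each dose/regimen combination". SAP 6.2 says regimen outright.

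**Who enters each phase (Protocol 3.3.1).** For dose escalation: "Subjects must have received and then progressed, or been intolerant to, at least one standard treatment regimen in the advanced or metastatic setting". This applies only where such a therapy exists, and subjects with documented refusal of, or ineligibility for, standard therapy may also enter. For the melanoma (MEL) expansion cohort: "Treatment naive subjects (ie, no prior systemic anticancer therapy for unresectable or metastatic melanoma").

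**How the SAP groups and checks melanoma.** SAP 7.1 has one melanoma category but splits NSCLC by prior anti-PD-1/PD-L1 therapy. SAP 7.2.3 lists prior systemic therapy for metastatic disease in the MEL expansion cohort as a relevant protocol deviation, meaning one that could affect how the results are interpreted.

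**The concern.** The MEL expansion cohort is defined by line of therapy so that its response rate describes untreated advanced disease. An escalation subject with melanoma on the matching regimen satisfies both matching factors whatever the treatment history. Such a subject would then count in the naive cohort's ORR, DOR and PFS, although the same history would be a relevant deviation in a subject enrolled directly into that cohort.

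The planned outputs would not make the mixture visible. The melanoma baseline summary in SAP 7.3.2 covers stage, M status, subtype, BRAF and PD-L1, but not prior therapy. The repeat analyses in SAP 7.5.1 name mutation status, HPV status and IPI score, and leave anything else to a general clause. At stake is how the melanoma estimates are read. Melanoma supplied 23 of the 25 responses reported in Protocol 1.5.

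**Working it through.** **Step 1: does a pretreated escalation subject fall into MEL?**

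- Disease type: melanoma. The row in Protocol Table 3.1.6-1 names the tumour only and does not mention treatment-naive status.
- Treatment: the same study regimen. Protocol Table 3.1.5-1 gives each cohort as one regimen with either weight-based or flat nivolumab, so the change to flat dosing does not by itself prevent a match.
- Could the subject belong to another melanoma cohort? The post-PD-1 cohort requires prior anti-PD-1/PD-L1 therapy. Exclusion 3(a) in Protocol 3.3.2 bars that therapy for escalation subjects but permits prior anti-CTLA4. A pretreated escalation subject therefore does not fit the post-PD-1 cohort.
- In the SAP, the only melanoma category is MEL.

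Under the rule as written, the subject goes into MEL.

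**Step 2: the plan's own figures.** Protocol 8.1.2.2 assumes n = 40 and a true ORR of 50%. Exact binomial tails give P(at least 15) = 96.0%, P(at least 17) = 86.6% and P(15 or fewer) = 7.7%, against the stated 96%, 87% and 8%. The one-sided 90% Clopper-Pearson lower limits for 7, 10 and 15 of 40 are 10.0%, 16.2% and 27.1%, against the stated 10%, 16% and 27%. All reproduce; none of these numbers is in dispute.

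**Step 3: effect of pooling on the expected ORR.**

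Inputs:
- 40 naive subjects with a 50% ORR (Protocol 8.1.2.2).
- k = pretreated melanoma subjects from escalation on the matching regimen. This is not given. The range is 0 to 12, because Protocol Table 3.1.5-1 allows up to 12 subjects per dose level across all tumour types.
- q = ORR in those subjects. This is not given; assumed range 10% to 40%.

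Formula: expected pooled ORR = (40 × 0.50 + k × q) / (40 + k).

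| k | q = 10% | q = 40% |
|---|---|---|
| 0 | 20/40 = 50.0% | 20/40 = 50.0% |
| 1 | 20.1/41 = 49.0% | 20.4/41 = 49.8% |
| 4 | 20.4/44 = 46.4% | 21.6/44 = 49.1% |
| 12 | 21.2/52 = 40.8% | 24.8/52 = 47.7% |

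For k of 1 to 4 the shift is 0.2 to 3.6 points. At the ceiling it is 2.3 to 9.2 points. For scale, the exact two-sided 95% interval for 20/40 runs from 33.8% to 66.2%.

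**The case against.** **Matching could mean matching to a cohort.** The Synopsis matches by tumour type, and the expansion table lists several melanoma and NSCLC groups under that heading. For NSCLC, where the SAP categories carry the prior-therapy distinction, this reading works. For melanoma it does not: neither the MEL row nor the SAP category carries the naive criterion, and 8.4.2 says disease type.

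**The SAP only permits pooling.** This is correct for SAP 6.2, which also does not name ORR. The firm instruction, including ORR, is the protocol's. The two documents therefore differ, and that needs settling too.

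**Escalation subjects need not be pretreated.** This stands in part. Intolerance qualifies as well as progression, and subjects with no available standard therapy, or with documented refusal or ineligibility, can enter. Some escalation melanoma subjects could be untreated.

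**The effect is small and nothing hinges on it.** Much of this stands. Reaching k = 12 needs every escalation subject at that dose level to have pretreated melanoma. Efficacy is secondary, there is no formal hypothesis, and entry to Stage 2 rests on at least 4 responses among the 20 Stage 1 expansion subjects (Protocol 3.1.6.1), not on the pooled rate. SAP 7.5.1 would also allow a repeat analysis by prior therapy, though it does not plan one.

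**The deviation list is beside the point.** Prior therapy in an escalation subject is not a deviation, so its absence from the list is proper. The list shows only that the SAP regards this characteristic as important for interpreting the MEL cohort.

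**Conclusion.** The point holds for treatment-naive melanoma. The protocol's matching rule omits prior therapy, the two phases have opposing general requirements on it, and the SAP has no category that would keep the groups apart. Under the stated assumptions the expected ORR falls from 50% to between 46.4% and 49.8% with 1 to 4 pretreated subjects, to between 40.8% and 47.7% at the ceiling of 12, and not at all if there were none. The melanoma count in escalation and the response rate in pretreated subjects are both unknown. This is a definition to tighten, not an error in any stated figure or decision rule.

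Three stronger readings are tempting but unsupported:

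- *That the two phases select opposite patients throughout.* NSCLC, SCCHN, DLBCL and FL expansion also require prior therapy, in the same direction as escalation. SCCHN has a narrower condition ("Tumor progression or recurrence within 6 months of last dose of platinum therapy"), but the documents give no basis for stating the direction or size of any bias there.
- *That the 23/46 melanoma result in Protocol 1.5 shows pooling has occurred, because 46 exceeds about 40.* The data cutoff of 30-Sep-2016 falls after Amendment 06 (09-May-2016) added the post-PD-1 melanoma cohort, and cohort sizes are approximate.
- *That all escalation subjects had failed earlier treatment.* The entry criteria do not require this.

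**What to change.** In Protocol 8.4.2, the Synopsis and SAP 6.2, match escalation to expansion subjects on disease type, study regimen and the prior-therapy criteria of the expansion cohort concerned (Protocol 3.3.1, 2(a)(ii)(1)). Show escalation subjects who do not meet those criteria in their own row, for example pretreated melanoma. Settle whether pooling *will* or *may* be done, and for which of ORR, DOR and PFS, and use the same wording in both documents.

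The cost is slightly fewer subjects in some pooled estimates. No new data should be needed, since the SAP already treats prior systemic therapy as a programmable check for the MEL expansion cohort; the same derivation would be applied to escalation subjects. The protocol wording needs an amendment with the usual IRB/IEC approval (Protocol 9.1.1), and could be carried with the next one while the SAP is changed first.

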8.4.3 Safety Analyses

All recorded adverse events will be listed and tabulated by system organ class, preferred term, tumor type, and treatment arm. Vital signs and clinical laboratory test results will be listed and summarized by tumor type and treatment arm. Any significant physical examination findings, and clinical laboratory results will be listed. ECG readings will be evaluated by the investigator and abnormalities, if present, will be listed.

8.4.4 Pharmacokinetic Analyses

Summary statistics will be tabulated for the pharmacokinetic parameters by tumor type, dose, regimen, study day and time on urelumab PK subjects and nivolumab PK subjects, where data is available. This data may also be pooled with other datasets for population PK analysis which will be part of a separate report.

[REDACTED]

[REDACTED]

[REDACTED]

[REDACTED]

[REDACTED]

[REDACTED]

[REDACTED]

8.4.6 *Outcomes Research Analyses*

Not applicable.

8.4.7 *Other Analyses*

A listing will be provided of all available immunogenicity data. Additionally, a listing of immunogenicity data from those subjects with at least one positive anti-drug antibody (ADA) at any time point will be provided by treatment for each analyte. Finally, the number (%) of subjects with the following anti-drug responses will be reported for each analyte if applicable, by dose, and overall: Baseline ADA Positive, ADA Positive (Persistent Positive, Only the Last Sample Positive), ADA Positive with Neutralizing Positive, and ADA Negative

To examine the potential relationship between immunogenicity and safety, the frequency and type of AEs of special interest may be summarized by overall immunogenicity status. Associations between trough concentrations of urelumab (or nivolumab) and corresponding ADA assessments may also be explored.

8.5 *Interim Analyses*

Data emerging from this study may be needed for timely decisions about adjustments to procedures in subsequent parts of the study. Therefore, data may be reviewed prior to the final lock of the study database. Additional interim analyses may also be performed for administrative purposes or publications. Analyses will only consist of listings, summaries, and graphs of the available data. No formal inferences requiring any adjustment to statistical significance level will be performed. Efficacy analyses based on interim data may use response evaluable or all treated populations depending on the purpose of the analysis.

9 STUDY MANAGEMENT

9.1 Compliance

9.1.1 *Compliance with the Protocol and Protocol Revisions*

The study shall be conducted as described in this approved protocol. All revisions to the protocol must be discussed with, and be prepared by, BMS. The investigator should not implement any deviation or change to the protocol without prior review and documented approval/favorable opinion from the IRB/IEC of an amendment, except where necessary to eliminate an immediate hazard(s) to study subjects.

If a deviation or change to a protocol is implemented to eliminate an immediate hazard(s) prior to obtaining IRB/IEC approval/favorable opinion, as soon as possible the deviation or change will be submitted to:

- IRB/IEC for review and approval/favorable opinion
- BMS
- Regulatory Authority(ies), if required by local regulations

Documentation of approval signed by the chairperson or designee of the IRB(s)/IEC(s) must be sent to BMS.

If an amendment substantially alters the study design or increases the potential risk to the subject: (1) the consent form must be revised and submitted to the IRB(s)/IEC(s) for review and approval/favorable opinion; (2) the revised form must be used to obtain consent from subjects currently enrolled in the study if they are affected by the amendment; and (3) the new form must be used to obtain consent from new subjects prior to enrollment.

If the revision is done via an administrative letter, investigators must inform their IRB(s)/IEC(s).

9.1.2 *Monitoring*

Representatives of BMS must be allowed to visit all study site locations periodically to assess the data quality and study integrity. On site they will review study records and directly compare them with source documents, discuss the conduct of the study with the investigator, and verify that the facilities remain acceptable. Certain CRF pages and/or electronic files may serve as source documents.

In addition, the study may be evaluated by BMS internal auditors and government inspectors who must be allowed access to CRFs, source documents, other study files, and study facilities. BMS audit reports will be kept confidential.

The investigator must notify BMS promptly of any inspections scheduled by regulatory authorities, and promptly forward copies of inspection reports to BMS.

9.1.2.1 *Source Documentation*

The Investigator is responsible for ensuring that the source data are accurate, legible, contemporaneous, original and attributable, whether the data are hand-written on paper or entered

electronically. If source data are created (first entered), modified, maintained, archived, retrieved, or transmitted electronically via computerized systems (and/or any other kind of electronic devices) as part of regulated clinical trial activities, such systems must be compliant with all applicable laws and regulations governing use of electronic records and/or electronic signatures. Such systems may include, but are not limited to, electronic medical/health records (EMRs/EHRs), adverse event tracking/reporting, protocol required assessments, and/or drug accountability records).

When paper records from such systems are used in place of electronic format to perform regulated activities, such paper records should be certified copies. A certified copy consists of a copy of original information that has been verified, as indicated by a dated signature, as an exact copy having all of the same attributes and information as the original.

9.1.3 *Investigational Site Training*

Bristol-Myers Squibb will provide quality investigational staff training prior to study initiation. Training topics will include but are not limited to: GCP, AE reporting, study details and procedure, electronic CRFs, study documentation, informed consent, and enrollment of WOCBP.

9.2 *Records*

9.2.1 *Records Retention*

The investigator must retain all study records and source documents for the maximum period required by applicable regulations and guidelines, or institution procedures, or for the period specified by BMS, whichever is longer. The investigator must contact BMS prior to destroying any records associated with the study.

BMS will notify the investigator when the study records are no longer needed.

If the investigator withdraws from the study (eg, relocation, retirement), the records shall be transferred to a mutually agreed upon designee (eg, another investigator, IRB). Notice of such transfer will be given in writing to BMS.

9.2.2 *Study Drug Records*

It is the responsibility of the investigator to ensure that a current disposition record of study drug (inventoried and dispensed) is maintained at the study site to include investigational product. Records or logs must comply with applicable regulations and guidelines and should include:

- amount received and placed in storage area
- amount currently in storage area
- label identification number or batch number
- amount dispensed to and returned by each subject, including unique subject identifiers
- amount transferred to another area/site for dispensing or storage
- non-study disposition (eg, lost, wasted)
- amount destroyed at study site, if applicable
- amount returned to BMS

- retain samples for bioavailability/bioequivalence, if applicable
- dates and initials of person responsible for Investigational Product dispensing/accountability, as per the Delegation of Authority Form.

BMS will provide forms to facilitate inventory control if the investigational site does not have an established system that meets these requirements.

